### 15.3.2.9 Section 9.7.1 Removal of thoracic impedance measurement

This section was changed as a result of Modification 2.

*Old text*

#### **VitalPatch biosensor**

VitalPatch biosensor will be provided by Bayer to sites. Subjects will wear the VitalPatch biosensor for overall 5 periods of 5 days each (for details on time periods see Table 1).

Parameters obtained from the VitalPatch biosensor are:

- ECG and parameters derived from ECG, like e.g. heart rate, HRV, AF burden, arrhythmias etc.
- Respiratory rate
- ~~Transcutaneous thoracic impedance = fluid status~~
- Skin temperature
- Step count
- Physical activity (duration and intensity)
- Posture

*New text*

### **VitalPatch biosensor**

VitalPatch biosensor will be provided by Bayer to sites. Subjects will wear the VitalPatch biosensor for overall 5 periods of 5 days each (for details on time periods see Table 9-1).

Parameters obtained from the VitalPatch biosensor are:

- ECG and parameters derived from ECG, like e.g. heart rate, HRV, AF burden, arrhythmias etc.
- Respiratory rate
- Skin temperature
- Step count
- Physical activity (duration and intensity)
- Posture

## **16. Appendices**

### **16.1 REALIsM-HF exploratory daily questionnaire to measure physical activity in heart failure - amended**

#### **Daily Patient-Reported Outcome Diary Items for REALIsM-HF Study**

##### Objectives

- Develop patient-reported outcome (PRO) items that can be administered as a daily diary in the REALIsM-HF pilot study
- Provide a brief high-level outline of how the PRO items can be used to:

- Validate activity monitoring data from wearable devices (VitalPatch biosensor and DynaPort Move Monitor)
- Measure symptom severity
- Facilitate the calculation of responder definitions/MIDs for activity and symptom data
- We hypothesized that “subjective” items generated from patient experiences (PRO, QoL) in combination with an (objective) activity monitor would capture all relevant dimensions of exercise capacity in patients with HFpEF and HFrEF and thus can be used as patient centric approach in clinical studies.

INSTRUCTIONS: We would like to know about your physical activities and heart failure symptoms in the past 24 hours. Physical activities are all activities that require “movement of your body,” such as walking, housework, and lifting objects. Please complete this questionnaire in the evening before going to bed. Please select the response that best applies to your physical activities and symptoms in the past 24 hours.

- 24 hour interval captures nighttime symptoms, such as orthopnea and PND
- Shorter instructions are ideal for daily assessment
- Need to develop a training module for use in hospital

---

 Replacement of AVIVO MPM with VitalPatch Biosensor as per Amendment 2 (Section 15.2)

Integrated Clinical Study Protocol  
19167

21 Feb 2020

Version. 4.0

Page: 106 of 108

ITEM	RESPONSE SCALE
How much time did you spend carrying or lifting objects in the past 24 hours?	Did not carry or lift objects 1-10 minutes 11-30 minutes 31-60 minutes Greater than 60 minutes
How much time did you spend walking outside of the house in the past 24 hours?	Did not walk outside of the house 1-10 minutes 11-30 minutes 31-60 minutes Greater than 60 minutes
How much time did you spend walking in general (in any location) in the past 24 hours?	Did not walk outside of the house 1-10 minutes 11-30 minutes 31-60 minutes Greater than 60 minutes
How much time did you spend doing housework or chores in the past 24 hours?	Did not do housework or chores 1-10 minutes 11-30 minutes 31-60 minutes Greater than 60 minutes
How many flights of stairs did you climb in the past 24 hours?	Did not climb stairs 1 flight of stairs 2 flights of stairs 3 flights of stairs 4 flights of stairs 5 flights of stairs 6 flights of stairs 7 flights of stairs 8 flights of stairs 9 flights of stairs 10 or more flights of stairs
How much time did you spend exercising in the past 24 hours?	Did not exercise 1-10 minutes 11-30 minutes 31-60 minutes Greater than 60 minutes
In general, how physically active were you in the past 24 hours?	Not active at all A little active Somewhat active Very active Extremely active

Integrated Clinical Study Protocol  
19167

21 Feb 2020

Version. 4.0

Page: 107 of 108

ITEM	RESPONSE SCALE
Please rate your worst tiredness at rest (when NOT doing physical activities) in the past 24 hours	Not Tired At All 0 1 2 3 4 5 6 7 8 9 10 Extremely Tired
Please rate your worst tiredness during physical activities in the past 24 hours	Not Tired At All 0 1 2 3 4 5 6 7 8 9 10 Extremely Tired
Please rate your worst shortness of breath at rest (when NOT doing physical activities) in the past 24 hours	No Shortness of Breath 0 1 2 3 4 5 6 7 8 9 10 Extreme Shortness of Breath
Please rate your worst shortness of breath during physical activities in the past 24 hours	No Shortness of Breath 0 1 2 3 4 5 6 7 8 9 10 Extreme Shortness of Breath
Please rate the worst swelling in your legs, ankles, or feet in the past 24 hours	No Swelling 0 1 2 3 4 5 6 7 8 9 10 Extreme Swelling
In general, how bad were your heart failure symptoms in the past 24 hours?	No Symptoms 0 1 2 3 4 5 6 7 8 9 10 Extreme Symptoms
INSTRUCTIONS	Now we would like for you to think about how your physical activities and symptoms have changed since you were discharged from the hospital.
How have your physical activities changed since you were discharged from the hospital?	Very much more physically active Much more physically active A little more physically active No change in physical activities A little less physically active Much less physically active Very much less physically active
How has your feeling of tiredness changed since you were discharged from the hospital?	Very much improved Much improved Minimally improved No change Worse Much Worse Very much worse
How has your shortness of breath changed since you were discharged from the hospital?	Very much improved Much improved Minimally improved No change Worse Much Worse

ITEM	RESPONSE SCALE
How has your swelling in your legs, ankles, or feet changed since you were discharged from the hospital?	
Very much worse
 
Very much improved                      Much improved                      Minimally improved                      No change                      Worse                      Much Worse                      Very much worse

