## 6. Study population

### 6.1 Inclusion criteria - amended

1. Written informed consent signed before any study-specific procedure
2. Men or women aged 45 years and older
3. Established diagnosis of chronic heart failure NYHA class II-IV
4. Worsening heart failure requiring hospitalization for the initiation of intensification of heart failure therapy with **at least one** of the following
  - BNP  $\geq$  100 pg/mL or NT-proBNP  $\geq$  400 pg/mL (sinus rhythm) or BNP  $\geq$  300 pg/mL or NT-proBNP  $\geq$  1200 pg/mL (atrial fibrillation)
  - Radiographic evidence of pulmonary congestion (interstitial edema, pulmonary venous hypertension, vascular congestion, pleural effusion)
  - Catheterization documented elevated filling pressures at rest (left ventricular end-diastolic pressure  $\geq$ 15 mmHg or pulmonary capillary wedge pressure  $\geq$ 20 mmHg) or with exercise (pulmonary capillary wedge pressure  $\geq$ 25 mmHg)

OR

Ambulatory patients with a history of heart failure on individually optimized treatment with HF medications unless contraindicated or not tolerated, for at least 12 weeks and **at least one** of the following

- Hospitalization for heart failure within the past 12 months or
- BNP  $\geq$  100 pg/mL or NT-proBNP  $\geq$  400 pg/mL (sinus rhythm) or BNP  $\geq$  300 pg/mL or NT-proBNP  $\geq$  1200 pg/mL (atrial fibrillation)

---

 Inclusion criteria extended to ambulatory subjects with chronic heart failure as per Amendment 3 (Section 15.3)

5. For HFrEF only
  - EF  $\leq$  35% assessed by any imaging modality (e.g. echocardiography, cardiac magnetic resonance, cine levocardiography) within 12 months prior to study inclusion
6. For HFpEF only
  - EF  $\geq$  45% assessed by any imaging modality (e.g. echocardiography, cardiac magnetic resonance, cine levocardiography) within 12 months prior to study inclusion
7. Willingness to wear the DynaPort Move Monitor accelerometer belt and VitalPatch biosensor during the trial
8. Body size allows wearing of the accelerometer belt as confirmed by ability to comfortably fasten the test belt provided for the screening process

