## 9.2 Visit description - amended

### Enrollment / Screening Visit - amended

Patients hospitalized with worsening HF will be asked to participate in this study; alternatively, also ambulatory patients can be enrolled. The investigator will inform the patient about the study. This will include discussing the consent form and asking the patient to read and – when agreeing to participate – sign the informed consent.

The following activities will be performed at the enrollment/screening visit after signing patient informed consent:

- Check for inclusion / exclusion criteria
- Recording of
  - Demographic data (including weight and height)
  - Medical and surgical history
  - Concomitant medication
  - Adverse events (AEs) including the use of healthcare resources (e.g. HF hospitalizations and urgent visits for HF)
- Recording of a 12-lead ECG
- Measurement of blood pressure and heart rate
- NYHA classification
- Blood sampling for biomarkers only for hospitalized patients

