## **KCCQ**

The KCCQ is the leading health-related quality-of-life measure for patients with HF. It was developed in the late 1990s to early 2000s by [name] at the Mid-America Heart Institute, Kansas City, MO, USA. It is a 23-item questionnaire that independently measures the impact of patients' HF, or its treatment, on 7 distinct domains:

1. Symptom Frequency – the KCCQ Symptom scale quantifies the frequency of clinical symptoms in HF, including fatigue, shortness of breath, paroxysmal nocturnal dyspnea, and edema / swelling.
2. Symptom Burden – the KCCQ Symptom burden scale quantifies the severity of clinical symptoms in HF, including fatigue, shortness of breath and edema / swelling.
3. Physical Limitation – the KCCQ Physical limitation scale measures the limitations patients experience, due to their HF, in performing routine activities.
4. Quality of Life – the KCCQ Quality of life scale is designed to reflect patients' assessment of their quality of life, given the current status of their HF.
5. Social Limitations – the KCCQ Social limitation scale quantifies the extent to which HF symptoms impair patients' abilities to interact in social roles.
6. Self-efficacy – numerous studies have underscored the importance of patients being engaged in the management of their disease. The KCCQ Self-efficacy scale quantifies patients' perception of how to prevent HF exacerbations and manage complications when they arise.
7. Symptoms Stability– unlike the other 5 domains that provide cross-sectional quantification of patients' current status, the KCCQ Symptom stability domain measures recent changes in patients' symptoms. As a measure of change, it is most interpretable as a baseline assessment of the stability of patients' symptoms at the start of the study and thereafter.

In addition, there are 3 summary scores, a Total Symptom Score that combines the Symptom Frequency and the Symptom Burden scores, a Clinical Summary Score that combines the Total Symptom and Physical Limitation scores to replicate the NYHA classification; and an Overall Summary Score that includes the Total Symptom, Physical Limitation, Social Limitations, and Quality of Life scores ([Figure 9-1](#)).

The exploratory daily QoL-Questionnaire is provided in Appendix 16.1.

KCCQ and PRO will be collected using electronic versions of the questionnaires on a tablet computer, which will be hand out to the patient for the duration of the study.

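### As printed, the daily questionnaire still dates change from hospital discharge after ambulatory entry was allowed, its general-walking item has an outdoor zero option, and SAP 6.5.2.2 puts a 2-unit fall in both classes

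*Protocol*

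**What the plan says.** **Change items.** Protocol 9.7.2 states that "The exploratory daily QoL-Questionnaire is provided in Appendix 16.1". In that appendix the block of change questions opens with "Now we would like for you to think about how your physical activities and symptoms have changed since you were discharged from the hospital". The activity item then asks "How have your physical activities changed since you were discharged from the hospital", and the tiredness, breathlessness and swelling items repeat the reference; the last reads "How has your swelling in your legs, ankles, or feet changed since you were discharged from the hospital". No alternative reference is offered.

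**Who can enter.** Since Amendment 3, inclusion criterion 4 (Protocol 6.1) also admits "Ambulatory patients with a history of heart failure on individually optimized treatment with HF medications". They must have "Hospitalization for heart failure within the past 12 months or" a natriuretic peptide above the stated limits, so a hospital stay is not required.

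**Use of the anchors.** SAP 6.5.2.2 takes over the five anchors of Appendix 16.1 and puts them in frequency tables. It names no grouping. The SAP cohorts are HFpEF and HFrEF, so a table by cohort would not separate entry settings either.

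**Walking items.** Appendix 16.1 has one item on outdoor walking and one on walking in any location. Both are printed with the same lowest option, which says only that the person took no walk outdoors. SAP 6.5.2.2 builds the Overall Activity Score from general walking, housework and exercise. The score goes into a mixed model and a worsening class, and SAP 6.5.4.1 uses that class for DynaPort subgroups.

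**Boundary.** SAP 6.5.2.2 counts a score decrease of 2 or more as worsening, and a decrease of no more than 2 as no worsening.

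**Mode.** Protocol 9.7.2 adds that "KCCQ and PRO will be collected using electronic versions of the questionnaires on a tablet computer". That electronic text is not in the documents.

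**The concern.** An impression-of-change item is interpretable only if respondents share a starting point. A patient who entered at discharge is asked about change since Visit 1. An ambulatory patient is asked about change since an event that may never have happened, or that happened at some other time. One table of all answers would mix these.

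The walking item has a different fault: two literally true answers to the same day. If a patient changes reading between the two diary periods, the score moves although walking did not. If the patient always picks zero, a real change in indoor walking is not recorded. Either effect can reach the worsening class and hence the DynaPort comparison. The overlap at exactly 2 units adds an arbitrary assignment at the cut-off.

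**Working it through.** The plan gives no figure of its own on this point, so there is none to reproduce.

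**1. Anchors tied to discharge**

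| Anchor (Appendix 16.1 and SAP 6.5.2.2) | Reference in the printed item |
|---|---|
| General physical activity | past 24 hours |
| Physical activity change | hospital discharge |
| Fatigue change | hospital discharge |
| Shortness of breath change | hospital discharge |
| Swelling change | hospital discharge |

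Count: 4 of 5.

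**2. Was the appendix revised for ambulatory entry?** Amendment 3 changed the reference to Visit 1 or discharge in the synopsis, in 9.1 and in the Visit 2 text, with footnotes that give ambulatory entry as the reason for 9.1 and Visit 2. Neither of its two lists of affected sections (15.3.1) contains 16.1. The amended label on 16.1 comes from the device replacement in Amendment 2. The discharge wording therefore looks carried over, not chosen.

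**3. What the reference means by entry route.** The first diary period runs from Visit 2 (Day 9 ± 2) to Day 16 ± 2, so Days 7 to 18. The second runs from Visit 3 (Day 77 ± 2) to Visit 4 (Day 84 ± 2), so Days 75 to 86.

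- Entered at discharge, no later admission: look-back of 7-18 and 75-86 days, and the reference is Visit 1.
- Ambulatory, qualifying by hospitalisation: up to 365 + 9 + 18 = 392 days and 365 + 9 + 86 = 460 days. The 9 is the maximum from screening to Visit 1. Counting the 12 months back from screening is an assumption.
- Ambulatory, qualifying by natriuretic peptide: no discharge is required, so the reference may be absent or have no upper limit.

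**4. Walking item.** Assume the five options are coded 0 to 4 (the documents give no coding) and the other two score items do not change. If a patient's k indoor-only days out of m diary days move between zero and true category c, the score shifts by c × k / m. The SAP threshold is a fall of at least 2. Appendix 16.1 averages over 7 days and requires at least 4.

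| True indoor time | c | Days needed, m = 7 | Days needed, m = 4 |
|---|---|---|---|
| 1-10 min | 1 | not reached (maximum 1.00) | not reached (maximum 1.00) |
| 11-30 min | 2 | 7 (2 × 7/7 = 2.00) | 4 (2 × 4/4 = 2.00) |
| 31-60 min | 3 | 5 (3 × 5/7 = 2.14) | 3 (3 × 3/4 = 2.25) |
| over 60 min | 4 | 4 (4 × 4/7 = 2.29) | 2 (4 × 2/4 = 2.00) |

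Three of these cells land on exactly 2.00, the value that the SAP puts in both classes. Minutes first and zero later gives false worsening; the reverse order gives false improvement or masks a real fall.

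**The case against.** **The printed text may not be what patients saw.** Parts of Appendix 16.1 read as a development outline, and the tablet version and the weekly questionnaire are not available to us. This stands. A reader might infer that recorded answers are defective; the documents show only that the printed instrument is.

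**Few patients may be affected.** Ambulatory entry became possible only with Amendment 3 of 21 February 2020, and at each centre only after local approvals (Protocol 13.1). SAP 4.1 dates the pandemic from 11 March 2020, 19 days later, and SAP 2 reports that recruitment stopped early. The group could be very small. This stands, and the number is not stated.

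**The change anchors carry little weight.** They enter frequency tables only. A reader might infer that responder definitions are undermined; Appendix 16.1 outlines such definitions, but the SAP plans none.

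**The walking scenarios are demanding.** They need assumed coding, many indoor-only days, mostly with more than 10 minutes' walking, and a change of reading. The instruction to choose the best-fitting response also favours a minutes band. This limits the likely frequency, but the two truthful answers remain.

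**Readmission.** One might argue that a readmission also moves the reference for discharge entrants. That was so before Amendment 3 and is not a failure to adapt to ambulatory entry. The readmission range in the Introduction is background, not an estimate for this study. Restricting analyses to subjects not readmitted would select on an event plausibly linked to worsening, and the records would miss some admissions: Protocol 9.6.1.1 exempts short and pre-planned stays from the SAE definition, and 9.6.3 ties healthcare use to AEs.

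**Conclusion.** The point holds for the printed documents and is minor. Four of the five anchors refer to a discharge that ambulatory entrants may not have had, or that is not their Visit 1, and the tables are planned without a split by entry setting. The general-walking item allows two truthful records of an indoor-only day and is one of three items in a score with downstream uses. A fall of exactly 2 units has no unique class.

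The day counts rest on the assumed 0-4 coding, on no change in the other two items and on a switch of reading between periods. Nothing in the documents shows that such switching occurred. The number affected and the direction of any bias are unknown, and all analyses are exploratory. A reader might go further and conclude that the DynaPort subgroup results are biased; the documents do not support that.

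**What to change.** 1. Compare the fielded tablet wording, including any translations, with Appendix 16.1 and record the result in the SAP or the study report.
2. For any remaining or future use, refer the change instruction and the four change items to Visit 1 or start of study, and give the general-walking item a zero option that means no walking at all.
3. If the wording was fielded as printed, tabulate the four change anchors in SAP 6.5.2.2 by entry setting, taken from the branch of criterion 4. The screening visit offers a cross-check, since Protocol 9.2 specifies "Blood sampling for biomarkers only for hospitalized patients". Read the split descriptively: ambulatory entry exists only after Amendment 3, so entry setting is tied to calendar time.
4. Report the number of diary days with both walking items at zero, by period and cohort. This is an upper limit for affected days, because a day with truly no walking is counted too. Do not exclude subjects on this count: a genuine fall to no walking is itself worsening, so exclusion would select on the outcome.
5. Assign a decrease of exactly 2 units to one class.

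The cost is one text check, one table split, one count and one boundary rule. Apart from the rewording, all of this can still be done although recruitment has stopped. The downside is small cells in the split tables.

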#### USE OF DIARY ITEMS TO VALIDATE ACTIVITY MONITOR

- Compare 1 week of activity monitor data with physical activity items from 1 week of diary monitoring
- Average diary data over 7 day period (must have  $\geq 4$  days to calculate a value)
- Physical Activity Diary Scores
  - Overall activity including carrying/lifting, walking outside, walking general, climbing stairs, housework, and exercise (average across items)
  - Individual item scores including general physical activity item
- Examine correlations between the activity monitor movement data and the physical activity diary scores

#### USE OF DIARY ITEMS TO CALCULATE RESPONDER DEFINITIONS

- Calculate average activity/symptom scores associated with change on anchor measures
- Anchor measures
  - General physical activity item (1 unit change on weekly average score)
  - Physical activity impression of change item (2 unit change)
  - Fatigue impression of change item (2 unit change)
  - Shortness of breath impression of change item (2 unit change)
  - Swelling impression of change item (2 unit change)
- Address using data from each weekly interval

AE	adverse event
CLIPS	clinical pharmacology standard
CSP	clinical study protocol
CSR	clinical study report
DES1 / DES2	device set 1 / 2
e.g.	exempli gratia (for example)
EU	European Union
FAS	full analysis set
HF	heart failure
HFpEF	heart failure with preserved ejection fraction
HFrEF	heart failure with reserved ejection fraction
HR	heart rate
i.e.	id est (that is)
KCCQ	Kansas City Cardiomyopathy Questionnaire score
MedDRA	Medical Dictionary for Regulatory Activities
NYHA	New York Heart Association
PA	physical activity
PAL	physical activity level
PRO	patient reported outcome
QoL	quality of life
QS	questionnaire for patient reported outcomes (daily and weekly)
SAP	statistical analysis plan
SD	Standard deviation
TEAE	treatment-emergent adverse event
TEE	total energy expenditure
WHO-DD	World Health Organization – drug dictionary

1. Introduction

Heart failure (HF) is known to be a major public health problem and a major cause of mortality and morbidity. It has a prevalence of up to 22% in elderly, and aging of population worldwide will result in a further rise in the HF prevalence by 50% over the next 10-15 years.

Heart failure with preserved ejection fraction (HFpEF) currently accounts for more than 50% of all HF cases and shows rising incidence, and outcomes among these patients are as poor as those with HF and reduced ejection fraction (HFrEF). Previous HF trials have focused primarily on reduction of cardiovascular mortality and/or readmission risk, whereas studies among hospitalized patients have largely focused on acute symptoms. Given the fact that patients with HFpEF are much older and have significant comorbidity burden compared to their peers with HFrEF, it is difficult to conceive that one drug or device can reduce mortality or hospitalization risk in these patients. Though intensively managed, these patients remain symptomatic and have substantially reduced functional capacity and quality of life (QoL).

QoL/patient reported outcome (PRO) and exercise capacity is an increasingly recognized patient and caregiver concern and may present more pragmatic outcomes, but are currently not typically considered as primary endpoints for clinical trials in HF patients.

This study aims to explore two devices providing a multi-marker biometrical monitoring including daily activity under real-life conditions in patients with HFpEF and HFrEF. It aims to identify potential new endpoints for future HFpEF trials by exploring clinically relevant changes over time and correlations/associations with conventional endpoints and biomarkers.

Furthermore, it aims to define the challenges and test the feasibility of this approach under real-life conditions.

This Statistical Analysis Plan (SAP) is based on the Clinical Study Protocol (CSP) No. BAY 1067197 / 19167, Version 4.0, dated 21 FEB 2020 [1].

2. Study Objectives

Primary objective:

- Measurement and quantification of daily physical activity (PA) in patients with HFpEF and HFrEF under real life conditions by activity tracker/belt and patch

Secondary objectives:

- Association between VitalPatch biosensor and DynaPort Move Monitor data (e.g. different levels of activity) to adverse events/clinical outcome data occurring during the study period
- Assess the baseline level and longitudinal changes over time of heart rate (HR), respiratory rate and ECG-derived parameters and the average of person-to-person physiological variability and the within-patient standard deviation between the baseline and 3-month measurements
- Assess the feasibility of activity tracking with two devices (VitalPatch biosensor and DynaPort Move Monitor) in patients with heart failure
- Correlation of activity data between VitalPatch biosensor data on activity and DynaPort Move Monitor¹
- Evaluate the relationship between physical activity levels, HR, respiratory rate and ECG-derived parameters and important measures in HFpEF; such as quality of life (QoL), patient reported outcome (PRO), biomarkers, outcomes (e.g. clinical endpoints such as hospitalization for heart failure, cardiovascular death, emergency visits)
- Support the development of HFpEF specific questions (PRO) for testing/validating cross-sectional and longitudinally
- Determine the variability of device derived biomarkers between subjects and within subjects over time in order to validate such biomarkers for clinical use in the context of heart failure
- Evaluate hs-copeptin as potential biomarker
- Correlation between patch monitor collected data and inpatient clinical data during hospital stay (e.g. echocardiography, weight gain/loss, NYHA, HR)²
- Explore the relationship between PA, 6-minute walking distance (6MWD), PRO, biomarkers, adverse events/clinical outcomes
- Investigate the accuracy of patients' self-reports (PRO, e.g. KCCQ) of time spent on PA in real life vs. objective assessment by the DynaPort Move Monitor and VitalPatch biosensor³

¹ Will not be addressed due to change from AVIVO to VitalPatch (ECG data only)

² Will not be addressed due to change in procedure schedule

³ Meaningful assessment not possible given the provided variables.

Given the data situation (not all parameters provided by the vendor) and the low number of subjects (recruiting stopped early due to recruiting issues), not all the original objectives mentioned above will be addressed.

3. Study Design

This is a non-randomized, multi-center, observatory prospective patient study. The study will be conducted in several centers in EU and non-EU.

[figure not shown]
Patients hospitalized due to heart failure as well as ambulatory patients with heart failure will be included in this study. Overall approx. 80 subjects have to complete at least all device monitoring periods:

- Approx. 60 subjects with established diagnosis of heart failure with preserved ejection fraction (HFpEF; EF ≥ 45%) (Cohort 1) and
- Approx. 20 subjects with established diagnosis of heart failure with reduced ejection fraction (HFrEF; EF ≤ 35%) (Cohort 2).

All patients will receive the AVIVO / VitalPatch biosensor at 5 monitoring periods (5 patches each subject in total, monitoring period 7 / 5 days each period) and the DynaPort Move Monitor (belt) at 2 monitoring periods (7 day monitoring each period). Results from both devices are not visible to investigator and subjects to avoid bias on treatment decisions.

Biomarkers will be investigated during the hospital stay (only in case patient is hospitalized), at visit 1, and at visit 4. A 6-minute walking test will be performed at visit 1 / discharge and after 11-12 weeks.

Design overview

Abbreviations: KCCQ = Kansas City Cardiomyopathy Questionnaire score; QS = Questionnaire for patient reported outcomes (daily and weekly); 6MWD = 6 minute walking distance; FUP = follow up visit

4. General Statistical Considerations

